Enrollment depends on the approval timelines, uptake, and treatment course in each country where the sites are open, as well as the total number of evaluable participants with PNH for AESIs. However, based on patient projections in selected countries, the MAH expects 300 participants with PNH to be enrolled with up to 7 years of follow-up during the duration of the Crovalimab Silo registry (7 years).

The IPIG aims to enroll approximately 25 participants with PNH who are pregnant in the Crovalimab Silo registry. Nevertheless, since the management of PNH during pregnancy has been challenging and pregnancy has been discouraged in participants with PNH, there are very few reported cases of pregnant participants with PNH treated with C5 inhibitors. For example, in a similar registry there were only 94 pregnancies in fewer than 1,086 females treated with eculizumab from June 2006 to November 2014 (Kelly et al. 2015; Höchsmann et al. 2022).

DATA ANALYSIS

No formal statistical testing will be performed. Descriptive statistics will be reported using summary tables and figures (where appropriate). Continuous variables will be summarized using mean, standard deviation, median, range (min–max) and interquartile range. Categorical variables will be summarized using counts and proportions (%).

Additionally, incidence and incidence rate (IRs; in person-years) and their 95% CIs of AESIs, SAEs and AEs will be calculated. The exact 95% CIs will be computed using the

Crovalimab—F. Hoffmann-La Roche Ltd
Protocol MO45473, Version 3.0

Clopper-Pearson method (Clopper and Pearson 1934). For the calculation of IRs, the denominator will be the pooled person-time of all the participants within the cohort. The patient time-at-risk will be calculated from index date until the date of an incident event or censoring, whichever occurs first. All first events occurring during follow-up period will be counted in the total number of events (thus, for each participant, only the first event will be counted) and divided by the total patient-years at risk. In addition to IRs, incidence proportions will be calculated as proportion of participants afflicted with each of the AESIs, SAEs, and AEs up to the data extraction date.

Subgroup and sensitivity analyses will be implemented when sample size allows.

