8.2 OBJECTIVES

The primary objectives for this study are as follows:

- To characterize and estimate the frequency of AESIs among participants with PNH exposed to crovalimab. AESIs are as follows:
 - Serious infections

- Meningococcal infection and other infections with encapsulated bacteria
- Development or worsening of any neurological condition (e.g., axonal neuropathy, multifocal mononeuropathy)
- Malignancies and hematologic abnormalities
- Serious hemolysis
- Transient immune complex reactions
- Infusion and injection-related reactions
- To characterize and estimate the frequency of AEs, SAEs, pregnancy outcomes, and infant outcomes in participants with PNH exposed to crovalimab during pregnancy and through breastfeeding. Specifically:
 - To estimate the frequency and further characterize all AEs, adverse pregnancy outcomes, and birth outcomes (during pregnancy until date of delivery), in pregnant female participants with PNH
 - To estimate the frequency and further characterize adverse fetal/neonatal/infant outcomes (e.g., major and minor congenital malformations, gestational age, postnatal growth and development) and SAEs at birth and through at least the first year of life of infants of mothers exposed to crovalimab during pregnancy
 - To estimate the frequency and further characterize all AEs for lactating females and infants exposed to crovalimab through breastfeeding

The secondary objectives for this study are as follows:

- To estimate the frequency and further characterize AEs and SAEs (not included as AESIs) in all participants with PNH exposed to crovalimab.
- To characterize clinical outcomes and laboratory test results relevant to PNH disease among participants with PNH who experienced an AESI
- To characterize patient-reported outcomes (PROs) among participants with PNH who experienced an AESI via a patient-reported fatigue assessment using the Functional Assessment of Chronic Illness Therapy (FACIT)-Fatigue questionnaire

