- Results in **persistent or significant disability/incapacity**: An event/reaction that results in a condition that substantially interferes with the activities of daily living of a study patient. Disability is not intended to include experiences of relatively minor medical significance such as headache, nausea, vomiting, diarrhea, influenza, and accidental trauma (e.g., sprained ankle).
- Is a **medically important event or reaction**: An important medical event/reaction that may not be immediately life-threatening or result in death or hospitalization, but based on medical judgment may jeopardize the patient and may require medical or surgical intervention to prevent any of the outcomes listed above (i.e., death of patient, life-threatening, hospitalization, prolongation of hospitalization, congenital anomaly/birth defect, or persistent or significant disability/incapacity). Examples of such events include allergic bronchospasm requiring intensive treatment in an emergency room or at home, blood dyscrasias or convulsions that do not result in inpatient hospitalization, or the development of drug dependency or drug abuse.
- Any suspected transmission via a medicinal product of an infectious agent is also considered as a SAE.

All AESIs, AEs, and SAEs will be recorded, including their corresponding dates and characteristics such as outcome, treatment, hospitalization, severity, seriousness, and de-/rechallenge.

9.3.1.3.2 Clinical Outcomes and Laboratory Test Results Relevant to PNH Among Participants who Experienced an AESI

The following clinical outcomes and laboratory test results related to PNH will be recorded among participants with PNH who experience an AESI:

- Major adverse vascular events (MAVEs), including thrombosis
 - If yes, type of event
- Red blood cell transfusions
 - Yes/No
 - Number of units received
- Breakthrough hemolysis (BTH)
 - Physician-defined BTH
 - Protocol-defined BTH
 - ≥ 1 new or worsening sign or symptom of intravascular hemolysis (fatigue, hemoglobinuria, abdominal pain, dyspnea, anemia [hemoglobin < 100 g/L], MAVE [including thrombosis], dysphagia, or erectile dysfunction) and elevated LDH ($\geq 2 \times$ the upper limit of normal [ULN]) after prior LDH reduction to $< 1.5 \times$ ULN on therapy
- High disease activity (HDA) status

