9.5 STUDY SIZE

Enrollment will depend on the approval timelines, uptake and treatment course in each country where the sites are open, as well as the total number of evaluable participants with PNH for AESIs (described in Section 9.3.1.2). However, based on patient projections in selected countries, the MAH expects 300 participants with PNH to be enrolled with up to 7 years of follow-up during the duration of the Crovalimab Silo registry (7 years).

[Table 2](#) provides probabilities (and associated 2-sided 95% CIs) to observe at least one event for AESIs with assumed prevalence ranging from 0.5%–20% in a population of 300 participants with PNH. For example, in the crovalimab trials, 6% of patients had a serious infection, 6.4% had an injection-related reaction, and 17.8% had a TICR, while no patients presented with a meningococcal infection or a serious hemolysis (Crovalimab E.U. Risk Management Plan [RMP] Version 1.0, 28 June 2024).

Table 2 Probability to Observe at least one Event for AESIs with Varying Prevalence

Assumed Prevalence ^a	Probability to Observe at least One AESI (95% CI)
0.5%	77.8% (10.2%–99.8%)
1.0%	95.1% (46.2%–100.0%)
1.5%	98.9% (74.3%–100.0%)
2.0%	99.8% (89.1%–100.0%)
5.0%	100.0% (100.0%–100.0%)
7.0%	100.0% (100.0%–100.0%)
10.0%	100.0% (100.0%–100.0%)
15.0%	100.0% (100.0%–100.0%)
20.0%	100.0% (100.0%–100.0%)

AESI = adverse event of special interest.

Note: 95% CIs are 2-sided and were calculated using Clopper-Pearson method (Clopper and Pearson 1934).

^a Assumed prevalence obtained during whole follow-up period.

In addition, the MAH aims to enroll approximately 25 participants with PNH who are pregnant in the Crovalimab Silo registry. Nevertheless, since the management of PNH during pregnancy has been challenging and pregnancy has been discouraged in participants with PNH, there are very few reported cases of pregnant participants with PNH treated with C5 inhibitors. For example, in a similar registry, there were only 94 pregnancies in fewer than 1,086 females treated with eculizumab from June 2006 to November 2014 (Kelly et al. 2015; Höchsmann et al. 2022).

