9.7.1 Safety Analyses

No formal statistical testing will be performed. Descriptive statistics will be reported using summary tables and figures (where appropriate). Continuous variables will be summarized using mean, standard deviation, median, range (min–max) and interquartile range. Categorical variables will be summarized using counts and proportions (%).

Additionally, incidence and incidence rate (IRs; in person-years) and their 95% CIs of AESIs, SAEs and AEs will be calculated. The exact 95% CIs will be computed using the Clopper-Pearson method (Clopper and Pearson 1934). For the calculation of IRs, the denominator will be the pooled person-time of all the participants within the cohort. The patient time–at-risk will be calculated from index date until the date of an incident event or censoring, whichever occurs first. All first events occurring during follow-up period will be counted in the total number of events (thus, for each participant, only the first event will be counted) and divided by the total patient-years at risk. In addition, to IRs, incidence proportions will be calculated as proportion of participants with PNH afflicted with each of the AESIs, SAEs, and AEs up to the data extraction date.

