11. MANAGEMENT AND REPORTING OF ADVERSE EVENTS/ADVERSE REACTIONS

This is a non-interventional PASS involving the use of secondary data and the reporting of adverse reactions in the form of individual Case Safety Reports (ICSRs) is not required.

Medical history and clinical outcomes, including adverse events, will be coded by System Organ Class and Preferred Term (PT) using the Medical Dictionary for Regulatory Activities (MedDRA®, the most recent version) lowest level term (LLT). Medications and vaccinations will be coded with the most recent edition of the WHO Drug Dictionary.

All adverse events extracted from the data source for the study as specified in the protocol will be summarized as part of any interim safety analyses and in the final study report and final publication.

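### Both defined frequency measures stop at each participant's first event, so neither describes repeat AESIs, SAEs or AEs; an all-episode rate should stand beside them

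*Protocol*

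**What the plan says.** Section 8.2 sets the first primary objective: "To characterize and estimate the frequency of AESIs among participants with PNH exposed to crovalimab". For the incidence rates of AESIs, SAEs and AEs, section 9.7.1 fixes the numerator ("thus, for each participant, only the first event will be counted") and the time at risk ("calculated from index date until the date of an incident event or censoring, whichever occurs first"). The synopsis repeats the rule: "for each participant, only the first event will be counted". The second measure is per participant as well: "incidence proportions will be calculated as proportion of participants with PNH afflicted with each of the AESIs, SAEs, and AEs". Section 9.7.2 lists subgroup and sensitivity analyses, none of which uses all episodes.

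The data would support more. Section 9.3.1.3.1 states: "All AESIs, AEs, and SAEs will be recorded, including their corresponding dates and characteristics". Section 11 adds: "All adverse events extracted from the data source for the study as specified in the protocol will be summarized", without naming a rate or a denominator. Section 9.5 gives the scale: "the MAH expects 300 participants with PNH to be enrolled with up to 7 years of follow-up".

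**The concern.** Several AESIs can happen more than once to the same person. Infusion and injection reactions are tied to each administration (9.3.1.2.7), and serious infections and hemolysis can recur during treatment that section 7 calls life-long. Under the stated rule, a participant leaves the risk set for an event type at its first occurrence.

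Two cases bear on safety concerns that section 7 attributes to the regulators:

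- **Hemolysis after discontinuation.** Section 9.2.3 continues follow-up after crovalimab is stopped (up to 12 months, or 12 weeks if a new complement inhibitor is started). A participant who had serious hemolysis on treatment is already out of the risk set, so a further episode in that window enters no rate.
- **TICR.** Section 7 says it can occur when switching to crovalimab and when switching away. A participant with a TICR on switching in cannot contribute a second one on switching out.

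At stake is whether the study can state how often these events happen per year of treatment, in addition to how many people ever have one.

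**Working it through.** **The plan's own figure.** Table 2 in section 9.5 gives the probability of at least one affected participant among 300. It reproduces: 1 − (1 − 0.005)^300 = 77.8%, and 1 − (1 − 0.01)^300 = 95.1%. It concerns occurrence per participant, so this point leaves it unchanged.

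**Inputs.** N = 300 (9.5). Proportion affected p = 6%, the trial figure for serious infection in 9.5, and p = 20%, the top of Table 2's range. Assumptions: p is cumulative over the whole follow-up, everyone has equal follow-up without dropout, and each person has a constant episode rate whose between-person variation is gamma with mean 1 and variance θ. The protocol gives no recurrence rate and no θ.

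**Formulas**, with follow-up scaled to 1 and μ the mean number of episodes per participant:

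- θ = 0: μ = −ln(1 − p). θ > 0: μ = [(1 − p)^(−θ) − 1]/θ.
- Share of episodes uncounted = 1 − p/μ.
- First-event rate = p/A, where A is the mean time at risk: p/μ for θ = 0; ln(1 + μ)/μ for θ = 1; otherwise [(1 + θμ)^(1 − 1/θ) − 1]/[μ(θ − 1)].
- Shortfall of the first-event rate against the all-episode rate = 1 − (p/A)/μ.

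**Results**

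| p | θ | μ | First events (300p) | All episodes (300μ) | Uncounted | A | Rate shortfall |
|---|---|---|---|---|---|---|---|
| 6% | 0 | 0.0619 | 18 | 18.6 | 3.0% | 0.970 | 0% |
| 6% | 1 | 0.0638 | 18 | 19.1 | 6.0% | 0.969 | 3.0% |
| 6% | 2 | 0.0659 | 18 | 19.8 | 8.9% | 0.969 | 6.0% |
| 6% | 10 | 0.0857 | 18 | 25.7 | 30.0% | 0.967 | 27.5% |
| 20% | 0 | 0.2231 | 60 | 66.9 | 10.4% | 0.896 | 0% |
| 20% | 1 | 0.2500 | 60 | 75.0 | 20.0% | 0.893 | 10.4% |
| 20% | 2 | 0.2813 | 60 | 84.4 | 28.9% | 0.889 | 20.0% |
| 20% | 4 | 0.3604 | 60 | 108.1 | 44.5% | 0.882 | 37.0% |

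One line in full (p = 6%, θ = 2): μ = (0.94^(−2) − 1)/2 = 0.0659; uncounted 1 − 0.06/0.0659 = 8.9%; A = (√1.1317 − 1)/0.0659 = 0.969; first-event rate 0.06/0.969 = 0.0619; shortfall 1 − 0.0619/0.0659 = 6.0%.

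**Reading.** With no between-person variation (θ = 0) the first-event rate equals the all-episode rate, because person-time stops together with the count; only the episode total is lost. The rates part when repeats cluster in susceptible participants. The constant-rate model suits TICR poorly, since TICR is tied to switching, so no size is claimed for it.

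**The case against.** The strongest reply is that nothing here is an error. A first-event rate with person-time stopped at that event is standard, its numerator and denominator match, and it estimates the rate of first occurrence. That stands, and it is why the rate should be kept. It can also be said that section 9.7.2 leaves full analysis details to the SAP. That carries less weight: the protocol does fix the counting rule, and fixes it for both frequency measures.

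Some stronger readings are tempting but lack support:

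- *Repeat events vanish from the study.* Rates come in addition to descriptive summaries (9.7.1), and section 11 promises a summary of all extracted events. Repeats are missing from the two defined measures; they may still appear as counts.
- *The rates draw mainly on early follow-up already covered by the trials.* At 6% affected, about 97% of person-time is retained (A above), and at 20% about 88% to 90%. The protocol gives no trial duration to compare with.
- *Time at risk ends at the first AE of any kind.* Section 9.7.1 refers to each of the AESIs, SAEs and AEs, and section 11 codes by Preferred Term, so rates by event type are a fair reading.
- *An event in a second pregnancy is certainly lost.* Pregnancy follow-up for women who conceive after enrollment runs from conception (9.2) and is censored at delivery (9.2.3), which suggests a clock per pregnancy. The counting rule nevertheless says per participant, so the unit needs stating. With about 25 pregnant participants planned, few second pregnancies are likely.

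**Conclusion.** The point holds as a gap in what the defined measures can show, and closing it is a cheap improvement. The incidence rate and the incidence proportion both answer how many participants are ever affected and how soon; neither answers how often the event happens. With events recorded by date and a primary objective framed as frequency, the second question can be answered from data already planned.

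The size is modest for rare AESIs: about 3% to 9% of episodes uncounted at 6% affected with frailty variance 0 to 2, and the first-event rate 0% to 6% below the all-episode rate. A shortfall near 27% at that frequency needs variance 10. For frequent or clustered events it grows, to 10% to 29% of episodes at 20% affected over the same variance range. All of this rests on the assumptions above.

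A reader might infer that a fifth to a half of episodes are lost in general. That needs assumed rates of 0.10 to 0.20 episodes per person-year over 4 years, which would affect 25% to 55% of participants. Section 9.5 reports 6% for serious infection, 6.4% for injection-related reaction and 17.8% for TICR, and no meningococcal infection or serious hemolysis, so the document does not support that as a general figure.

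**What to change.** In section 9.7.1 and the synopsis:

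1. Keep the first-event rate and the incidence proportion, and state that they describe first occurrence.
2. For serious infections, IRRs, serious hemolysis, TICR, SAEs and AEs, add the all-episode rate: total episodes divided by total follow-up time to censoring, not stopped at the first event. Give a confidence interval that allows for within-participant correlation (robust variance or negative binomial).
3. In the pregnancy cohort, state that first event is applied per pregnancy.

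No new data collection is needed. The cost is additional tables and a simple rule for separating a new episode from continuation of an old one. Onset and resolution dates are planned for infections, hemolysis and TICR (9.3.1.2.1, 9.3.1.2.2, 9.3.1.2.5 and 9.3.1.2.6). For IRRs the administration is the natural separator, and the rule should say how local and systemic reactions to the same dose are counted, since 9.3.1.2.7 records them separately. For very rare AESIs the added rate will differ little from the first-event rate.

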9.2 SETTING

This study will analyze individual patient-level data gathered from multiple countries within the Crovalimab Silo. To date, the Crovalimab Silo plans to enroll participants from

Belgium, Canada, France, Germany, Italy, Netherlands, South Korea, Spain, United Kingdom, and the United States. China is under feasibility.

Index Date

The index date is defined as follows:

- To evaluate AESIs and other SAEs and AEs for all participants with PNH, the index date will be defined as the date of enrollment in the Crovalimab Silo.
- To characterize SAEs and AEs for women who are pregnant and pregnancy outcomes, the index date for these outcomes will be defined based on the pregnancy status at the time of silo enrollment. If the participant with PNH is pregnant, the index date will be the date of the silo registry enrollment. If the participant with PNH becomes pregnant after enrollment, the index date will be defined as the date of conception (DOC).
- To assess adverse fetal/neonatal/infant outcomes, SAEs, and AEs at birth and through at least the first year of the infant's life, the index date will be defined as the date of infant birth.
- For breastfeeding-related safety events, the index date will be defined as the date of initiation of breastfeeding for women who are in the Crovalimab Silo before breastfeeding starts or as the date of enrollment for women who join the Crovalimab Silo while breastfeeding.

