9.2.3 Participant Follow-up

The follow-up period will be the time period from index date (as defined in Section 9.2.1) until the end of the study or censoring, whichever comes first.

To evaluate AESIs and other AEs and SAEs for all participants with PNH, the date of censoring will be defined as the earliest occurrence of any of the following events:

- Consent withdrawal
- Site termination
- Crovalimab treatment discontinuation¹ (with an extra follow-up period after discontinuation)
- Enrollment into an interventional clinical trial²
- Death

To assess safety events during pregnancy and breastfeeding, including pregnancy and infant outcomes, additional censoring events will be defined:

- Date of delivery (for pregnancy safety and outcomes)
- First year of the infant's life (for safety and infant outcomes)
- On the date when breastfeeding stops or first year of the infant's life (for breastfeeding)

[figure not shown]
¹ For participants with PNH censored due to crovalimab treatment discontinuation, follow-up will continue up to 12 months if the participant does not start a new complement inhibitor or for 12 weeks if the participant starts a new complement inhibitor.

² To preserve the integrity of data collected for any interventional therapy for PNH in clinical studies, as well as to avoid duplicate safety reporting, participant data collection will be paused from the Crovalimab Silo and the Core Registry when participants enroll in an interventional clinical study for a PNH therapy.

Note: Safety events from the mother will continue to be recorded even after pregnancy ends, delivery, or the cessation of breastfeeding. Similarly, infant safety events will also continue to be recorded through their first year of age if breastfeeding is suspended.

Evaluation of pregnancy and infant outcomes during crovalimab exposure will rely on prospectively collected data within the Crovalimab Silo only for participants who enroll into the silo before being pregnant. However, for participants who enroll into the Crovalimab Silo while being pregnant, retrospective data on crovalimab exposure and outcomes will be incorporated into the silo, if such data are available from the Core Registry. Data for participants whose pregnancy outcomes occur before their enrollment in the Crovalimab Silo will not be obtainable. Very few instances are expected in these latter two scenarios due to the timing of drug approvals and site initiations in the Core Registry (see Figure 3).

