9.7.2 Subgroup and Sensitivity Analyses

Subgroup and sensitivity analyses will be implemented when sample size allows.

Analyses will be presented separately for all participants with PNH, for pregnant female participants with PNH, for all infants, and for infants sub-grouped by breastfeeding status (yes/no).

When feasible, analyses will be further detailed according to each trimester of pregnancy and each quarter within the infant's first year of development.

To account for previous complement inhibitor exposure, subgroup analyses will be also based on previous PNH treatment exposure, using the following definitions: "naïve new users" when individuals initiate crovalimab without prior exposure to C5 inhibitors, and "Prevalent new users" when individuals initiate crovalimab after having received at least one C5 inhibitor any time prior to crovalimab treatment start. Safety events will be also described by causality.

Potential confounding factors influencing safety and pregnancy outcomes, such as demographic information (e.g., age, race/ethnicity), clinical characteristics, maternal medical history, obstetrical history, comorbidities, and concomitant medications will be described among participants with PNH who experience an AESI, as well as for pregnancy or infant outcomes. If needed, subgroup analysis will be performed and AESIs proportions and incidence rates will be compared between subgroups.

Similarly, subgroup analysis may include clinical and laboratory test outcomes for PNH (e.g., MAVEs, HDA, BTH, etc.) and previous PNH treatment.

Sensitivity analysis will be performed restricting the data to safety events and crovalimab exposure that was collected prospectively only. The effects of the timing of crovalimab exposure before and during pregnancy and cumulative exposure periods on each outcome will be also evaluated as sensitivity analysis. Sensitivity analysis may also include timing variations of FTT and development deficiency outcomes, when available.

Full details on all statistical analyses, including other subgroup and sensitivity analyses, will be described in the Statistical Analysis Plan (SAP).

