9.9.4 Loss to Follow-up

Given the maximum follow-up duration of 7 years, the study may experience a significant proportion of discontinued participants. To detect potential biases, the characteristics of these discontinued participants will be compared with those who complete the registry. Specific Concerns for PNH and Pregnancy In parallel, the MAH will explore options to renegotiate with the IPIG registry if needed to extend the study duration, ensuring a minimum five-year follow-up is met for all enrolled participants with PNH and pregnant participants with PNH are included. Likewise, the MAH will investigate alternative approaches for data collection to supplement enrollment if necessary.

Potential confounding factors affecting pregnancy outcomes will be assessed and contextualized, particularly those related to PNH treatment. It is unlikely that participants with PNH who are pregnant will stop crovalimab therapy entirely due to the severity of PNH relapses.

Moreover, existing evidence suggests PNH is associated with certain pregnancy complications and adverse outcomes, indicating that PNH itself may act as a confounder in the relationship between crovalimab and pregnancy-related outcomes evaluated in this study. Residual confounding from unmeasured factors is anticipated, and its impact on study outcomes cannot be predicted.

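### The incidence proportion in Protocol 9.7.1 has no time horizon or censoring adjustment, so for events that accrue over time it depends on length of follow-up and should not be compared across reports or subgroups

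*Protocol*

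**What the plan says.** Protocol 9.7.1 (and the synopsis) defines two frequency measures for AESIs, SAEs and AEs.

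- **Incidence rate:** first events divided by person-time, which runs "from index date until the date of an incident event or censoring, whichever occurs first".
- **Incidence proportion:** the "proportion of participants with PNH afflicted with each of the AESIs, SAEs, and AEs up to the data extraction date". No horizon, minimum follow-up or adjustment for censoring is given.

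The design around these measures:

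- For the all-participant analysis, 9.2 sets entry individually: "the index date will be defined as the date of enrollment in the Crovalimab Silo".
- Section 9.2.3 follows each participant "until the end of the study or censoring, whichever comes first". Censoring events are consent withdrawal, site termination, crovalimab discontinuation with an extra window, entry into an interventional trial, and death. After discontinuation, "follow-up will continue up to 12 months if the participant does not start a new complement inhibitor", or for 12 weeks if one is started.
- Section 9.5 states that "the MAH expects 300 participants with PNH to be enrolled with up to 7 years of follow-up" and calls treatment switching common. Section 9.9.4 warns that "the study may experience a significant proportion of discontinued participants".
- Section 6 schedules annual interim reports from Q4 2026 to Q4 2031 and a final report in Q4 2032.
- Section 9.7.2 says that, if needed, "AESIs proportions and incidence rates will be compared between subgroups".

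**The concern.** A crude share of participants affected is a clear quantity only when everyone has been observed for about the same time. Here observed time can run from almost nothing to more than six years. On the natural reading of the definition, someone who enrolled a month before extraction, or who was censored after a few months, counts in the denominator as fully as someone followed for six years.

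Three uses are at risk:

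- reading the proportion as a risk, when no period is attached to it;
- comparing it from one interim report to the next, when it climbs as follow-up lengthens;
- comparing it between subgroups under 9.7.2, when a difference in follow-up can look like a difference in safety.

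The definition is written into the protocol, and it serves the primary objective of estimating AESI frequency.

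**Working it through.** **The plan's own figure.** The protocol gives no number for the incidence proportion. The nearest is Table 2 in 9.5, the probability of at least one event in 300 participants, 1 − (1 − p)^300. For p = 0.5%, 1.0%, 1.5% and 2.0% this gives 77.8%, 95.1%, 98.9% and 99.8%, as printed. The table's footnote ties p to the whole follow-up period, so it too carries no fixed horizon.

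**Inputs for the check**

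- From the protocol: registry start Q1 2026 and last extraction Q2 2032 (9.1), so T = 6.25 years; n = 300 (9.5).
- Assumed, because the protocol gives no figure: uniform entry over A = 3 to 5 years; drop-out at a constant rate d = 0.05 to 0.15 per year, not separating death from other exits; constant event hazard λ; interim data cuts in the quarter of each report. The 15% risk is an illustration within the 0.5 to 20% range of Table 2.

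**Formula.** A true 5-year risk of 15% gives λ = −ln(0.85)/5 = 0.0325 per year. With k = λ + d, the expected crude proportion at time T is

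P = (λ/k) × {1 − [exp(−k(T − A)) − exp(−kT)]/(kA)}.

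At cuts before accrual ends, A is replaced by T.

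**Worked case, A = 5, d = 0.10, T = 6.25.** k = 0.1325 and λ/k = 0.2453. exp(−0.1325 × 1.25) = 0.847 and exp(−0.1325 × 6.25) = 0.437. The bracket divided by kA is 0.4105/0.6625 = 0.620. P = 0.2453 × 0.380 = 9.3%.

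**Final extraction, true 5-year risk 15%**

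| Entry period | d = 0.05 | d = 0.10 | d = 0.15 |
|---|---|---|---|
| 3 years | 12.7% | 11.4% | 10.2% |
| 4 years | 11.5% | 10.4% | 9.4% |
| 5 years | 10.3% | 9.3% | 8.5% |

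The gap to 15% is 2.3 to 6.5 points. For scale, the binomial standard error of 15% at n = 300 is √(0.15 × 0.85/300) = 2.1 points.

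**Drift at constant hazard (A = 5, d = 0.10).** The proportion reads 1.2% at 0.75 years (Q4 2026), 4.0% at 2.75 years, 6.3% at 4.75 years and 9.3% at 6.25 years. The expected rate stays at 3.25 per 100 person-years throughout.

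**Wider assumptions.** Take a 6% risk at 6.25 years, entry over 2 to 6.25 years and drop-out of 0 to 20% per year. The final crude value is then 2.1 to 5.1%.

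**Subgroups.** Take two groups with the same λ and d = 0.10, one entering uniformly in years 0 to 2 and the other in years 3 to 5. They read 12.3% and 6.3% at the final extraction. These entry windows are hypothetical.

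**The case against.** The strongest reply is that this is mostly a matter of labelling. Much of it stands.

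- **A reader might infer that the proportion is biased downward as a risk.** The protocol names no horizon, so there is no target to be biased against. With the hazard used above, the 1-, 2- and 3-year risks are 3.2%, 6.3% and 9.3%. The worked final value of 9.3% is therefore about right for three years and low only for longer horizons. What stands is that the figure has no defined period.
- **A reader might infer that the rate and the proportion count different events**, because one stops at censoring and the other at extraction. Section 9.2.3 defines one follow-up period and data collection largely ends at censoring, so few later events could enter. The extraction date can simply be read as the data cut-off.
- **A reader might infer that event frequency cannot be estimated properly.** The person-time rate is planned alongside and handles unequal follow-up under constant hazard. It averages over time, however, so it does not give the risk by a stated duration.
- **A reader might infer that naive and prevalent new users will show a spurious difference.** Nothing in the protocol says that they enter at different times, and 9.7.2 compares subgroups only if needed and reports rates with the proportions. It is a possibility, not a prediction.
- **The effect is not general.** It is small for events clustered at treatment start or switch. Two of the three AESIs with a non-zero trial frequency in 9.5 are of this kind: injection-related reactions (6.4%) and TICRs (17.8%).

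That no formal testing is planned does not answer the point: a descriptive frequency still needs a time frame.

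**Conclusion.** The point holds in a limited form. As fixed in 9.7.1, the incidence proportion is a crude fraction over unequal follow-up. For events that accrue over time it moves with the extraction date and with each subgroup's follow-up, so it should not carry comparisons across interim reports or subgroups.

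Under the stated accrual and drop-out ranges, a true 5-year risk of 15% would read about 8 to 13% at the final extraction. That size rests on assumed uniform entry, constant hazard and drop-out unrelated to the event. Early entry with little drop-out would shrink it, and informative drop-out could change it either way. The documents do not support calling the study's frequency estimation invalid, since the rate is sound for its own purpose. This is an inexpensive improvement to the estimator and its labelling.

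**What to change.** In 9.7.1, for AESIs, SAEs and AEs in the all-participant cohort:

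1. Add cumulative incidence at fixed times from the index date, for example 1, 3 and 5 years where numbers at risk allow, with 95% CIs. Use the Aalen-Johansen estimator and the censoring dates of 9.2.3, except that death is treated as a competing event.
2. Use this estimate and the incidence rates, not the crude proportion, for subgroup comparisons under 9.7.2 and for reading across interim reports.
3. Keep n/N as a count labelled crude, with median follow-up beside it.
4. Keep n/N for pregnancy and infant outcomes. Their follow-up is bounded by delivery or the infant's first year, so 3- and 5-year horizons have no meaning there.

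The cost is slightly more analysis work and wide intervals at late times, when few participants remain at risk. Enrollment, event, discontinuation and withdrawal dates are already to be collected, so no new data item is needed.
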